11.5.6 Contraception and Pregnancy

The effects of VX-445 monotherapy or in TC with TEZ and IVA on conception, pregnancy, and lactation in humans are not known. VX-445, TEZ, and IVA did not show genotoxic potential in a standard battery of in vitro (Ames test, chromosomal aberration, or micronucleus in cultured mammalian cells) and in vivo (rodent micronucleus) studies. Reproductive toxicology studies of VX-445, TEZ, and IVA have not shown teratogenicity in rats and rabbits.

11.5.6.1 Contraception

Contraception requirement for a couple is waived for the following:

- True abstinence for the subject, when this is in line with the preferred and usual lifestyle of the subject. Periodic abstinence (e.g., calendar, ovulation, symptothermal, postovulation methods) and withdrawal are not acceptable methods of contraception. True abstinence must be practiced from the date of informed consent through 90 days after the last dose of study drug.
- If the male is infertile (e.g., bilateral orchiectomy). If a male subject is assumed to have complete bilateral absence of the vas deferens, infertility must be documented before the first dose of study drug (e.g., examination of a semen specimen or by demonstration of the absence of the vas deferens by ultrasound).
- If the female is of non-childbearing potential. To be considered of non-childbearing potential, the female must meet at least 1 of the following criteria:
 - Postmenopausal: Amenorrheic for at least 12 consecutive months and a serum follicle-stimulating hormone (FSH) level within the laboratory's reference range for postmenopausal females
 - Documented hysterectomy or bilateral oophorectomy/salpingo-oophorectomy

Note: All other females (including females with tubal ligations) will be considered to be of childbearing potential.

- Same-sex relationships

For subjects for whom the contraception requirement is not waived, study participation requires a commitment from the subject that at least 1 acceptable method of contraception is used as a couple. Methods of contraception must be in successful use from signing of consent (or

assent, when applicable), approximately 28 days before the first dose of study drug (unless otherwise noted), and until 90 days following the last dose of study drug. Additional contraception requirements may need to be followed according to local regulations and/or requirements. Acceptable methods of contraception are listed in [Table 11-2](#).

Table 11-2 Acceptable Methods of Contraception

	Male Subjects and Their Female (Non-study) Partners	Female Subjects and Their Male (Non-study) Partners
Vasectomy performed at least 6 months previously, with a documented negative postvasectomy semen analysis for sperm	Yes	Yes
Bilateral tubal occlusion (e.g., ligation) performed at least 6 months previously	Yes	Yes
Male or female condom with or without spermicide ^a	Yes	Yes
Female barrier contraception (such as diaphragm, cervical cap, or sponge) with spermicide	Yes	Yes
Continuous use of an intrauterine device for at least 90 days before the first dose of study drug		
Hormone-releasing	Yes	Yes
Non-hormone releasing	Yes	Yes
Oral, implanted, injected, or vaginal hormonal contraceptives, if successfully used for at least 60 days before the first dose of study drug	Yes	Yes

^a A female condom cannot be used with a male condom due to risk of tearing.

Additional notes:

- If over the course of the study the subject meets the criteria for waiving the contraception requirements, the subject does not need to follow the contraceptive methods listed in [Table 11-2](#).
- If over the course of the study the subject's status changes and the subject does not meet the criteria for waiving the contraception requirements, the subject must begin following the contraceptive methods listed in [Table 11-2](#).
- Male subjects must not donate sperm during the period starting from the first dose of study drug until 90 days after the last dose of study drug.
- Female subjects should not nurse a child during the period starting from the first dose of study drug until 90 days after the last dose of study drug.
- For male subjects with a female partner of childbearing potential, the couple should not plan to become pregnant during the study or within 90 days after the last dose of study drug, with the exception of couples who plan to become pregnant by artificial insemination using sperm banked by the male subject before the first dose of study drug or sperm from another source.

11.5.6.2 Pregnancy

Subjects will be counseled to inform the investigator of any pregnancy that occurs during study treatment and for 90 days after the last dose of study drug.

If a subject, or the female partner of a male subject, becomes pregnant during study participation, study drug will be permanently discontinued immediately. The investigator will 1) notify the medical monitor and Vertex Global Patient Safety (GPS) within 24 hours of the site's knowledge of the subject's (or partner's) pregnancy, and 2) send the Pregnancy Information Collection Form to Vertex GPS. Male subjects with female partners who become pregnant during the study must use a male condom to avoid exposure of a potential embryo or fetus to study drug via the seminal fluid.

Provided informed consent is obtained, the subject or partner will be followed until the end of the pregnancy and the infant will be followed for 1 year after the birth. A separate ICF will be provided to explain these follow-up activities. Pregnancy itself does not constitute an AE.

12 STATISTICAL AND ANALYTICAL PLANS

This section presents a summary of the planned analyses for this protocol. Statistical analysis details will be provided in the statistical analysis plan (SAP), which will be finalized before the clinical data lock for the study.

12.1 Sample Size

The primary and secondary objectives of the study are the evaluation of the long-term safety, tolerability, and efficacy of VX-445/TEZ/IVA. This is an open-label study that will enroll subjects who complete study treatment in the parent study and meet eligibility criteria. Approximately 56 subjects are expected to enroll in this open-label study.

12.2 Analysis Sets

The following analysis sets will be defined for Part A and Part B separately:

The **Open-label All Subjects Set** for Part A or B is defined as all subjects who were enrolled (defined as subject having data in the corresponding clinical database) in the corresponding Part. This analysis set will be used for individual subject data listings and disposition summary tables unless otherwise specified.

The **Open-label Full Analysis Set (OL-FAS)** for Part A or B is defined as all enrolled subjects who have received at least 1 dose of study drug in the corresponding Part. The OL-FAS will be used to summarize subject demographics and baseline characteristics and for all efficacy analyses unless otherwise specified.

The **Open-label Safety Set (OL-SS)** for Part A or B is defined as all subjects who have received at least 1 dose of study drug in the corresponding Part. The OL-SS will be used for all safety analyses unless otherwise specified.

12.3 Statistical Analysis

12.3.1 General Considerations

Continuous variables will be summarized using the following descriptive summary statistics: the number of subjects (n), mean, SD, median, minimum value (min), and maximum value (max). The precision of the measurement for each continuous variable will be specified in the SAP. Unless otherwise specified, min and max values will be reported with the same precision as the units of the raw data. The mean, median, and SD will be reported to 1 additional decimal

place. Any values that require a transformation to standard units (metric or SI) will be converted with the appropriate precision.

Categorical variables will be summarized using counts and percentages. Percentages will be presented to 1 decimal place.

The baseline value, unless otherwise specified, will be the most recent non-missing measurement (scheduled or unscheduled) collected before the first dose of study drug in the parent study. For assessments collected in replicates, the baseline will be defined as the average of non-missing values.

Change (absolute change) from baseline will be calculated as post-baseline value – baseline value.

The **Efficacy Analysis Period** for each Part will include the time from the first dose of study drug to the last scheduled efficacy visit in the corresponding Part, unless otherwise specified.

The **Treatment-emergent (TE) Period** for each Part will include the time from the first dose of study drug to 28 days after the last dose of the study drug or to the date of completion of study participation in the corresponding Part (as defined in Section 9.1.5), whichever occurs first.

Part A and Part B data will be analyzed separately, using the respective analysis set, efficacy analysis period, and TE period for each Part. For analysis of the number of PEx, events in the parent study and this study (Parts A and B, as applicable) may also be combined.

12.3.2 Background Characteristics

12.3.2.1 Subject Disposition

Subject disposition will be summarized separately for each Part for the Open-label All Subjects Set. The number and percentage of subjects in the following categories will be summarized as appropriate:

- Open-label All Subjects Set
- Dosed (OL-SS)
- Enrolled and dosed (OL-FAS)
- Completed treatment
- Prematurely discontinued treatment and the reasons for discontinuation
- Completed study
- Prematurely discontinued the study and the reasons for discontinuation

12.3.2.2 Demographics and Baseline Characteristics

Demographics and baseline characteristics will be summarized separately for each Part by descriptive summary statistics. Baseline characteristics will be the same as the parent study baseline characteristics.

The following demographics and baseline characteristics will be summarized for the OL-FAS and will include (but are not limited to) sex, race, ethnicity, baseline age, baseline weight, baseline height, baseline BMI, baseline ppFEV₁, baseline SwCl, and baseline CFQ-R RD score.

Medical history will be summarized by MedDRA System Organ Class (SOC) and Preferred Term (PT) for the OL-FAS.

12.3.2.3 Prior and Concomitant Medications

Medications will be coded using WHODrug and categorized as follows:

- **Prior medication:** any medication that was administered within the 56 days before the first dose of study drug in each Part
- **Concomitant medication:** medication continued or newly received during the TE Period in each Part
- **Post-treatment medication:** medication continued or newly received after the TE Period in each Part

A given medication may be classified as a prior medication, a concomitant medication, or a post-treatment medication; both prior and concomitant; both concomitant and post-treatment; or prior, concomitant, and post-treatment. If a medication has a missing or partially missing start/end date or time and if it cannot be determined whether it was taken before initial dosing, concomitantly during the TE Period, or beyond the TE Period, it will be considered in all 3 categories of prior, concomitant, and post-treatment medication.

Prior medications and concomitant medications will be summarized descriptively by Preferred Name based on the OL-FAS, separately for each Part. Post-treatment medications will be provided separately in an individual subject data listing.

12.3.2.4 Study Drug Exposure and Compliance

Study drug exposure will be summarized separately for each Part based on the OL-SS, defined as the last day of study drug in each Part minus the first day of study drug in each Part plus 1, regardless of study drug interruption.

Study drug compliance will be summarized based on the OL-FAS, and will be calculated as: $100 \times [1 - (\text{total number of days of study drug interruption in each Part}) / (\text{duration of study drug exposure in days in each Part})]$. A study drug interruption on a given day is defined as an interruption of any study drug on that day.

In addition, percentage of tablets taken will also be summarized based on the OL-FAS, and will be calculated as: $100 \times [(\text{total number of tablets dispensed in each part}) - (\text{total number of tablets returned in each Part})] / (\text{total number of tablets planned to be taken per day} \times \text{duration of study drug exposure in days for each Part})$.

12.3.2.5 Important Protocol Deviations

An important protocol deviation (IPD) is a deviation that may significantly affect the completeness, accuracy, or reliability of the study data or that may significantly affect a subject's rights, safety, or wellbeing. The rules for identifying an IPD will be described in the SAP.

All IPDs will be provided in an individual subject data listing, and summarized, as appropriate.

12.3.3 Efficacy and Pharmacodynamic Analyses

The secondary objective of the study is the evaluation of the long-term efficacy and PD of VX-445/TEZ/IVA.

12.3.3.1 Analysis of Primary Endpoint

Not applicable. Efficacy and PD are not primary objectives.

12.3.3.2 Analysis of Secondary Efficacy and Pharmacodynamic Endpoints

The secondary endpoints will be analyzed separately for each Part.

- Absolute change in ppFEV₁**

One of the secondary efficacy endpoints is the absolute change from baseline in ppFEV₁ at visits in this open-label study, for subjects who receive at least 1 dose of study drug in each Part. The primary analysis for this secondary endpoint will be based on a mixed-effects model for repeated measures (MMRM), with the absolute change from baseline in ppFEV₁ as the dependent variable for visits in each Part. The model will be similar to the one used in the parent study.

The details including sensitivity analyses and supportive analysis will be described in the SAP.

- Absolute change in SwCl**

Analysis of this PD endpoint will be based on an MMRM similar to the one used in the parent study.

- Absolute change in CFQ-R RD score**

Analysis of this endpoint will be based on an MMRM similar to the one used in the parent study.

- Absolute change in BMI and BMI-for-age z-score**

Analysis of this endpoint will be based on an MMRM similar to the one used in the parent study.

- Number of PEx and CF-related hospitalizations**

Analysis of this endpoint will be based on summary statistics. Additional analysis may be provided and details will be discussed in the SAP.

- Absolute change in LCI_{2.5}**

Analysis of this endpoint will be based on an MMRM similar to the one used in the parent study.

- Absolute change in weight and weight-for-age z-score**

Analysis of this endpoint will be based on an MMRM similar to the one used in the parent study.

- Absolute change in height and height-for-age z-score**

Analysis of this endpoint will be based on an MMRM similar to the one used in the parent study.

12.3.3.3 Multiplicity Adjustment

Not applicable.

12.3.4 Safety Analysis

The primary objective of the study is the evaluation of the long-term safety and tolerability of VX-445/TEZ/IVA. Data from Part A and Part B will be analyzed separately. For each Part, all safety analyses will be based on the TE Period for subjects in the OL-SS, unless otherwise specified.

The overall long-term safety profile of study drug will be assessed in terms of the following safety and tolerability endpoints:

- Incidence of treatment-emergent adverse events (TEAEs)
- Clinical laboratory values (i.e., serum chemistry, hematology, coagulation, and urinalysis)
- ECGs
- Vital signs
- Pulse oximetry

All safety data will be presented in individual subject data listings. Only descriptive analyses of safety data will be performed.

12.3.4.1 Adverse Events

For analysis purposes, AEs will be classified as pretreatment AEs, TEAEs, or post-treatment AEs, defined as follows:

- **Pretreatment AE:** any AE that occurred before the first dose of study drug in the TE Period in each Part
- **TEAE:** any AE that worsened (either in severity or seriousness) or newly developed at or after the first dose date of study drug in the TE Period in each Part
- **Post-treatment AE:** any AE that worsened (either in severity or seriousness) or newly developed after the TE Period in each Part

For AEs with missing or partial start dates, if there is no clear evidence that the AEs started before or after study drug treatment, then the AEs will be classified as TEAEs.

AE summary tables will be presented for TEAEs only and will include the following:

- All TEAEs
- TEAEs by strongest relationship
- TEAEs by maximum severity
- TEAEs leading to treatment discontinuation
- TEAEs leading to treatment interruption
- Serious TEAEs
- TEAEs leading to death
- Grade 3 and Grade 4 TEAEs
- Frequently reported TEAEs

Summaries will be presented by MedDRA SOC and PT using frequency counts and percentages (i.e., number and percentage of subjects with an event). When summarizing the number and percentage of subjects with an event, subjects with multiple occurrences of the same AE or a continuing AE will be counted once, only the maximum severity level will be presented in the severity summaries, and the strongest relationship level in the relationship summaries. An AE

overview table will be provided. In addition, a listing containing individual subject level AE data for all deaths and other serious and significant AEs will be provided separately. All AEs, including pre- and post-treatment AEs, will be presented in individual subject data listings.

Exposure-adjusted event rates may also be provided.

12.3.4.2 Clinical Laboratory Assessments

For the treatment-emergent laboratory measurements, the observed values and change from baseline values of the continuous laboratory parameters will be summarized in SI units at each time point during the TE Period in each Part.

The number and percentage of subjects with at least 1 threshold analysis event during the TE Period in each Part will be summarized. The shift of the threshold analysis criteria from baseline to post-baseline will also be summarized for selected laboratory parameters. The threshold analysis and parameter selection criteria will be provided in the SAP.

Results of urinalysis and pregnancy tests will be listed in individual subject data listings only. In addition, a listing containing individual subject laboratory assessment values will be provided. This listing will include data from scheduled and unscheduled time points.

Additional safety laboratory data analyses may be described in the SAP.

12.3.4.3 Electrocardiogram

For the treatment-emergent ECG measurements, a summary of observed values and change from baseline values will be provided at each time point during the TE Period in each Part, for the following standard 12-lead ECG interval measurements (in msec): RR, PR, QT, QTc for heart rate (HR) interval (QTcF), QRS duration, and HR (beats per minute).

The number and percentage of subjects with at least 1 threshold analysis event during the TE Period in this open-label study will be summarized. The threshold analysis criteria will be provided in the SAP.

Additional ECG analyses may be described in the SAP.

12.3.4.4 Vital Signs

For the treatment-emergent vital signs measurements, the observed values and change from baseline values will be summarized at each time point during the TE Period in each Part. The following vital signs parameters will be summarized: systolic and diastolic blood pressure (mm Hg), body temperature (°C), pulse rate (beats per minute), and respiratory rate (breaths per minute).

The number and percentage of subjects with at least 1 threshold analysis event during the TE Period in each Part will be summarized. The threshold analysis criteria will be provided in the SAP.

Additional vital signs analyses may be described in the SAP.

12.3.4.5 Pulse Oximetry

For the treatment-emergent pulse oximetry measurements, a summary of observed values and change from baseline values will be provided at each time point during the TE Period in each Part, for the percent of oxygen saturation by pulse oximetry.

The number and percentage of subjects with shift changes from baseline (normal/missing and low according to the reference range) to the lowest percent of oxygen saturation during the TE Period will be summarized.

12.3.4.6 Physical Examination

No tables/figures/listings will be provided for PE data.

12.3.4.7 Other Safety Analyses

Details of other safety analyses may be included in the SAP.

12.3.5 Other Analyses

Details of other analyses, including FE-1 and IRT, will be provided in a separate document.

12.3.6 Interim and IDMC Analyses

12.3.6.1 Interim Analysis

Interim analyses may take place at any time at the discretion of the sponsor.

12.3.6.2 IDMC Analysis

The IDMC (Section 9.1.6) will conduct regular safety reviews of study data as outlined in the IDMC charter.

The IDMC's objectives, responsibilities, and operational details will be defined in a separate document (IDMC charter), which will be finalized before the first subject is enrolled in the study.

13 PROCEDURAL, ETHICAL, REGULATORY, AND ADMINISTRATIVE CONSIDERATIONS

13.1 Adverse Event and Serious Adverse Event Documentation, Severity Grading, and Reporting

13.1.1 Adverse Events

13.1.1.1 Definition of an Adverse Event

An AE is defined as any untoward medical occurrence in a subject during the study; the event does not necessarily have a causal relationship with the treatment. This includes any newly occurring event or worsening of a pre-existing condition (e.g., increase in its severity or frequency) after the ICF is signed.

An AE is considered serious if it meets the definition in Section 13.1.2.1.

13.1.1.2 Clinically Significant Assessments

Study assessments including laboratory tests, ECGs, PEs, and vital signs will be assessed and those deemed to have clinically significant worsening from baseline will be documented as an AE. When possible, a clinical diagnosis for the study assessment will be provided, rather than the abnormal test result alone (e.g., urinary tract infection, anemia). In the absence of a diagnosis, the abnormal study assessment itself will be listed as the AE (e.g., bacteria in urine or decreased hemoglobin).

An abnormal study assessment is considered clinically significant if the subject has 1 or more of the following:

- Concomitant signs or symptoms related to the abnormal study assessment
- Further diagnostic testing or medical/surgical intervention
- A change in the dose of study drug or discontinuation from the study

Repeat testing to determine whether the result is abnormal, in the absence of any of the above criteria, does not necessarily meet clinically significant criteria. The determination of whether the study assessment results are clinically significant will be made by the investigator.

A laboratory value that is Grade 4 will not automatically be an SAE. A Grade 4 laboratory value will be an SAE if the subject's clinical status indicates a life-threatening AE.

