9.7 Dose Modification for Toxicity

Modifications of the study drug dose are prohibited. Should any unacceptable toxicity arise, individual subjects will be withdrawn from the study and dosing will cease.

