9.8.1 Liver Function Tests

The central laboratory will notify the medical monitor of alanine transaminase (ALT) or aspartate transaminase (AST) $>3 \times$ upper limit of normal (ULN) and total bilirubin $>2 \times$ ULN that are derived from centrally submitted samples.

Subjects with new treatment-emergent ALT or AST elevations of $>3 \times$ ULN, with or without total bilirubin $>2 \times$ ULN, must be followed closely, including confirmatory testing performed by

the central laboratory within 48 to 72 hours of the initial finding and subsequent close monitoring of ALT, AST, and bilirubin levels, as clinically indicated.

If a subject cannot return to the site for confirmatory testing, a local laboratory may be used. Local laboratory results must be reported immediately to the medical monitor, and the subject must have the tests repeated and sent to the central laboratory as soon as possible (ideally within 48 to 72 hours).

Study drug administration **must be interrupted** immediately (prior to confirmatory testing) if any of the following criteria are met:

- ALT or AST $>8 \times$ ULN
- ALT or AST $>5 \times$ ULN for more than 2 weeks
- ALT or AST $>3 \times$ ULN, in association with total bilirubin $>2 \times$ ULN and/or clinical jaundice

A thorough investigation of potential causes should be conducted, and the subject should be followed closely for clinical progression.

Study drug administration **must be discontinued** if the following criteria are met:

- Subsequent ALT or AST values confirm the initial elevation that satisfied the interruption rule (above), and no convincing alternative etiology (e.g., acetaminophen use, viral hepatitis, alcohol ingestion) is identified, regardless of whether transaminase levels have improved

All subjects in whom treatment is discontinued for elevated transaminases (and bilirubin, as applicable) should have these levels monitored closely until levels normalize or return to baseline.

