10.4.2.1 Adverse Events

For analysis purpose, AEs will be classified as pretreatment AEs, TEAEs, or post-treatment AEs, defined as follows:

- **Pretreatment AE:** any AE that occurred before the first dose date of study drug in the OLE Safety Period.
- **TEAE:** any AE that worsened (either in severity or seriousness) or that was newly developed at or after the first dose date of study drug through the end of the OLE Safety Period.
- **Post-treatment AE:** any AE that worsened (either in severity or seriousness) or that was newly developed after the OLE Safety Period.

For AEs with completely missing or partially missing start dates, if there is no clear evidence that the AEs were pretreatment or post-treatment, the AEs will be classified as TEAEs.

Details for imputing missing or partial start dates of adverse events are defined in Appendix D.

An overview of all TEAEs during OLE Safety Period will be provided with the following categories:

- Number of TEAEs (total number of TEAEs only)

- Subjects with any TEAEs
- Subjects with TEAEs by strongest relationship
- Subjects with TEAEs by maximum severity
- Subjects with TEAEs leading to study drug discontinuation (discontinuation of any study drug)
- Subjects with TEAEs leading to study drug interruption (interruption of any study drug)
- Subjects with grade 3/4 TEAEs
- Subjects with related TEAEs
- Subjects with serious TEAEs
- Subjects with related serious TEAEs
- Subjects with TEAEs leading to death

The frequency counts and percentages as well as the exposure adjusted event rate will be presented for the above overview table. The exposure adjusted rate will not be presented for strongest relationship and maximum severity categories.

The following summary tables of TEAEs during OLE Safety Period will be presented:

- All TEAEs
- TEAEs leading to treatment discontinuation
- TEAEs leading to treatment interruption
- Serious TEAEs
- TEAEs leading to death
- Grade 3/4 TEAEs
- TEAEs by strongest relationship
- TEAEs by maximum severity
- Related TEAEs
- Related serious TEAEs

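### The third criterion for a clinically significant test result names a prohibited dose change and leaving the study, but not interrupting or stopping study drug, so a small set of result-driven interruptions or stops could go unrecorded as AEs

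*Protocol*

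**What the plan says.** Protocol 13.1.1.2 treats an abnormal assessment as clinically significant, and so as an AE, if at least one of three things applies:

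1. related signs or symptoms;
2. "Further diagnostic testing or medical/surgical intervention";
3. "A change in the dose of study drug or discontinuation from the study".

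It adds two qualifications: "Repeat testing to determine whether the result is abnormal, in the absence of any of the above criteria, does not necessarily meet clinically significant criteria", and "The determination of whether the study assessment results are clinically significant will be made by the investigator". Sections 11.5.2 (laboratory) and 11.5.4 (ECG) make AE reporting depend on clinical significance.

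On dosing, section 9.7 states "Modifications of the study drug dose are prohibited" and says that, for unacceptable toxicity, "individual subjects will be withdrawn from the study and dosing will cease". Section 9.8.1 requires interruption for specified transaminase results "immediately (prior to confirmatory testing) if any of the following criteria are met", and discontinuation of study drug in defined circumstances. Section 11.5.4 has subjects stop dosing on a QTcF value above threshold.

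The SAP's safety overview (10.4.2.1) has a row that begins "Subjects with TEAEs leading to study drug interruption (interruption of any study drug" and a matching row for discontinuation. The Part A analysis (SAP 10.4.1.1) has the same rows. All of them count treatment-emergent AEs (TEAEs).

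**The concern.** The third criterion appears meant to catch results serious enough to affect treatment, but the actions it names do not match those the protocol uses. A dose change is not available as a response to toxicity. Leaving the study is not the same as stopping study drug. Interruption and discontinuation of study drug, which the protocol does use, are absent.

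Safety and tolerability are the primary endpoint, and the TEAE rows are where a reader looks for treatment halted by a safety finding. If a result halts dosing but no AE is recorded, the subject is not counted there. The special-interest summary for elevated transaminases (SAP 10.4.2.9.1) also depends on reported AE terms.

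**Working it through.** No figure in the plan bears on this, so the check compares the texts.

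**Do the omitted actions fall under the words used?** The protocol keeps the categories apart.
- Section 9.9 distinguishes withdrawing from the study from being withdrawn from study drug treatment.
- Section 12.3.2.1 counts premature treatment discontinuation and premature study discontinuation on separate lines; SAP 10.2.2.1 does the same.
- Table 13-3 lists dose reduction, interruption and withdrawal of drug as three different actions.

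Reading interruption as a kind of dose change therefore does not fit the protocol's own terms. The dose changes planned in 9.1 follow weight and age, not test results.

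**Which cases meet a listed criterion?**

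| Situation | Relevant section | Listed criterion met? |
|---|---|---|
| Transaminase interruption with a work-up for cause | 9.8.1 | Usually the second |
| Any interruption over 72 hours | 9.8 calls for investigation of the cause before resumption | Usually the second |
| Unacceptable toxicity handled as 9.7 words it | 9.7, withdrawal from the study | The third |
| Asymptomatic value, pause of 72 hours or less, repeat test only | The investigation in 9.8 is not triggered | None |
| QTcF above threshold, dosing stopped, only repeat ECGs done | 11.5.4 | None clearly; arguable |

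**What do the planned outputs still show if no AE is recorded?**
- The value: laboratory and ECG threshold tables (SAP 10.4.2.2, 10.4.2.3, Appendix E) and individual listings that include unscheduled visits.
- A treatment discontinuation: disposition with reasons, by Part, plus a listing (SAP 10.2.2.1).
- An interruption: days in the compliance calculation (SAP 10.2.2.6).
- The link between an interruption and the result that caused it: no planned table.

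**Size.** SAP 7.2 gives 64 enrolled subjects. If all were dosed and so form the safety set, each missed subject changes a row by 1/64 = 0.0156, or 1.6 percentage points. The documents do not allow the number of missed subjects to be estimated.

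**The case against.** The strongest reply is that the other criteria and the investigator's judgement already do the work. The list says what is sufficient, not what is exclusive: a result is significant if a criterion applies, not only if one does. The investigator decides, the AE definition in 13.1.1.1 is broad, and Table 13-3 lets a recorded AE carry an interruption or withdrawal as the action taken. Section 9.8 extends the investigation of cause to every interruption over 72 hours, not just those for liver tests. For QTcF, hourly ECGs after the value has been confirmed arguably go beyond checking whether it is abnormal, and so may count as further testing. Section 11.5.1 promises AE form completion guidelines and training, which are not visible here and may already cover the point.

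Most of this stands, and it narrows the gap to the last two rows of the table. It does not close it. A rule that leaves the case to judgement permits two sites to record the same event differently, and the criterion best placed to settle the matter omits the relevant actions.

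Two stronger readings are tempting. A reader might infer that an interruption without an AE is visible only as lost compliance days, and that a stop without an AE is lost altogether. The documents do not support this: the values remain in threshold tables and listings, and treatment discontinuations remain in disposition. A reader might also infer that the primary safety tables do undercount. The text shows only that they could.

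**Conclusion.** The wording gap is real and its reach is small. Interruption and discontinuation of study drug are missing from the third criterion, although they are the protocol's actual responses to test results. The residual set is mainly an asymptomatic value with a pause of 72 hours or less and only repeat testing, and arguably a QTcF-driven stop with only repeat ECGs. Such cases need not become AEs and could be absent from the TEAE rows for interruption or discontinuation.

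This is a possible undercount, not a demonstrated one. It assumes that the investigator applies the list as written and records no AE on judgement alone, and that the unseen form guidelines do not already require one. Severity is minor.

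**What to change.** Reword the third criterion of 13.1.1.2 to: interruption or permanent discontinuation of study drug, or discontinuation from the study, because of the result. This matches the action categories in Table 13-3. Carry the same instruction into the AE form guidelines.

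Before database lock, reconcile every interruption or discontinuation recorded as due to a test result against a linked AE, and query those without one. This can be done even if the protocol is not amended, provided the dosing record captures the reason for the interruption.

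The change concerns AE recording only and alters no stopping or interruption rule. It costs one protocol line, a guideline entry and a data-management check. The downside is a few more AEs recorded.
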